 - Events which require intervention with immunosuppressant therapy, steroids, surgery, or hormone replacement generally require permanently stopping study treatment.
- c. Permanently discontinue ipilimumab for any of the following:
- Persistent adverse reactions that require holding more than 2 treatment doses.
 - Any related Grade 3 or 4 event (see exceptions below)
 - Any event that requires immunosuppressive treatment or systemic steroids which cannot be discontinued during the time in which it takes to hold more than 2 treatment doses
 - Severe or life-threatening adverse reactions, including any of the following:
 - Colitis with abdominal pain, fever, ileus, or peritoneal signs; increase in stool frequency (7 or more over baseline), stool incontinence, need for IV hydration for more than 24 hours, gastrointestinal hemorrhage, and gastrointestinal perforation

- Aspartate aminotransferase (AST) or alanine aminotransferase (ALT) >5 times the upper limit of normal or total bilirubin >3 times the upper limit of normal
- Stevens-Johnson syndrome, toxic epidermal necrolysis, or rash complicated by full thickness dermal ulceration, or necrotic, bullous, or hemorrhagic manifestations
- Severe motor or sensory neuropathy, Guillain-Barré syndrome, or myasthenia gravis
- Severe immune-mediated reactions involving any organ system (e.g., nephritis, pneumonitis, pancreatitis, non-infectious myocarditis)
- Immune-mediated ocular disease that is unresponsive to topical immunosuppressive therapy
- Any adverse event, laboratory abnormality or intercurrent illness which, in the judgment of the investigator, presents organ specific injury and/or a substantial clinical risk to the patient with continued dosing.

NOTE: The following neurological adverse events require permanent discontinuation of ipilimumab and define unacceptable neurotoxicity:

- Any motor neurologic toxicity \geq Grade 3 regardless of causality
- Any \geq Grade 3 treatment related sensory neurologic toxicity

Please refer to [Appendix 18.3](#) and [Appendix 18.4](#) for specific treatment algorithms.

- d. Exceptions to Permanent Discontinuation of Ipilimumab
- Potentially reversible inflammation (< Grade 4), attributable to a local anti-tumor reaction and a potential therapeutic response. This includes inflammatory reactions at sites of tumor resections or in draining lymph nodes, or at sites suspicious for, but not diagnostic of metastasis.

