 - Hospitalization for \leq Grade 2 adverse events where the primary reason for hospitalization is to expedite the clinical work-up.
 - Patients with the following conditions where in the treating investigator's opinion continuing study drug administration is justified based on the potential for continued clinical benefit:
 - Patients treated with systemic steroids for less than 2 weeks without evidence of autoimmune disease requiring steroids treatment
 - Grade 2 skin rash treated with topical steroids for less than 4 weeks
 - Grade 2 ocular toxicity that has completely responded to topical therapy within 4 weeks
 - Endocrinopathies where clinical symptoms are controlled with appropriate hormone replacement therapy. **Note:** Ipilimumab may not be restarted while the patient is being treated with systemic corticosteroids except for patients on stable doses of hormone replacement therapy such as hydrocortisone.
- e. Allowance for ipilimumab dose delay
- In general, patients who meet criteria to resume ipilimumab will also have met criteria to resume nivolumab with ipilimumab, so it should be feasible to synchronize dosing of both drugs when resuming ipilimumab. In order to facilitate this, the dosing calendar days of nivolumab and ipilimumab may be adjusted within a +/- 5 day window, as long as consecutive nivolumab doses are given at least 12 calendar days apart.
 - If an ipilimumab dose is delayed beyond 6 weeks from the prior ipilimumab dose, then subsequent nivolumab doses should be rescheduled to maintain at least a 3-week interval between consecutive ipilimumab doses.

- Dosing delays to manage drug-related adverse events, such as prolonged steroid tapers, are allowed. Disease assessments should continue as per protocol even if dosing is delayed.
- Dosing delays resulting in no ipilimumab dosing for > 6 weeks that occur for non-drug-related reasons may be allowed if approved by the Study Chairs. Disease assessments should continue as per protocol even if dosing is delayed.
- In event of any Grade 2 adverse event experienced while on combination nivolumab plus ipilimumab therapy, patient may resume treatment/may be continued on nivolumab monotherapy alone, at the discretion of the treating investigator
- Ipilimumab will not be given as monotherapy for Arm 2.

NOTE: If adverse events result in permanent discontinuation of ipilimumab, then subsequently manage dose delays under Management/Next Dose for nivolumab alone

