8.4 Dose Delay Criteria for Nivolumab in Combination with Ipilimumab (Arm 2)

Dose modifications for nivolumab in combination with ipilimumab by adverse event type are detailed in [Table 8.1](#). General considerations for dose modifications are as follows.

For the initial induction period, patients with Grade 2 or 3 events requiring discontinuation of treatment with the combination may consider continuing treatment with single agent nivolumab when the event resolves to baseline. However, patients with renal, CNS, or pulmonary toxicity must be removed from study.

- a. In addition to the AEs identified in the table below, ipilimumab and nivolumab dose should be delayed for any AE, laboratory abnormality or inter-current illness which, in the judgment of the treating investigator, warrants delaying the dose of study medication.
- b. Patients requiring a delay of > 6 weeks or who experience immune-related toxicity with inability to decrease prednisone ≤ 10 mg PO daily must go off protocol therapy entirely.
- c. Patients who received systemic corticosteroids for management of any drug-related immunologic toxicity must be off corticosteroids or have tapered down to an equivalent dose of prednisone 10 mg/day.
- d. Nivolumab monotherapy may be continued at treating investigator discretion if there is evidence of clinical benefit. In this event, patient will continue nivolumab until AE is resolved and ipilimumab may be re-started or if ipilimumab is permanently discontinued (in congruence with guidelines in table below), then patient will continue nivolumab alone until cycles are completed. At completion of 4 cycles, patient may continue on nivolumab alone, as per protocol. If ipilimumab is permanently discontinued prior to receipt of 4 doses, nivolumab dosing should remain at the Cycle 1-4 dosing (1 mg/kg every 2 weeks) until completion of Cycle 4 and should then switch to Cycle 5+ dosing (480 mg every 4 weeks).

Table 8.1 Dose Modification for Related Adverse Events

Treatment-related Adverse Event	Grade of Event	Nivolumab and/or Ipilimumab
Nausea	≤ Grade 1	No dose modification
	Grade 2	Hold until ≤ Grade 1 OR baseline (exceptions as noted below) ¹
	Grade 3	Off protocol therapy (exceptions as noted below) ¹
	Grade 4	Off protocol therapy
*Patients requiring a delay of >2 weeks must go off protocol therapy.		
Recommended management: antiemetics.		
Diarrhea (immune-related enterocolitis)	≤ Grade 1	No dose modification

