	Grade 2	Hold until ≤ Grade 1 OR baseline (exceptions as noted below) ¹
	Grade 3	Off protocol therapy (exceptions as noted below) ¹
	Grade 4	Off protocol therapy
*Patients requiring a delay of >2 weeks must go off protocol therapy		

Recommended management: Loperamide antidiarrheal therapy Dosage schedule: 4 mg at first onset, followed by 2 mg with each loose motion until diarrhea-free for 12 hours (maximum dosage: 16 mg/24 hours) Adjunct anti-diarrheal therapy is permitted and should be recorded when used. See GI AE Algorithm for management of symptomatic colitis. Patients with Grade 2 symptoms but normal colonoscopy and biopsies may be retreated after resolution. Patients who require steroids must be taken off study treatment. Please evaluate pituitary function prior to starting steroids if possible without compromising acute care. Evaluation for all patients for additional causes includes C. diff, acute and self-limited infectious and foodborne illness, ischemic bowel, diverticulitis, and IBD.
		
Vomiting	≤ Grade 1	No dose modification
	Grade 2	Hold until ≤ Grade 1 OR baseline (exceptions as noted below) ¹
	Grade 3	Off protocol therapy (exceptions as noted below) ¹
	Grade 4	Off protocol therapy
*Patients requiring a delay of >2 weeks must go off protocol therapy.		
Recommended management: antiemetics.		
Other GI	≤ Grade 1	No dose modification
	Grade 2	Hold until ≤ Grade 1 OR baseline (exceptions as noted below) ¹
	Grade 3	Off protocol therapy (exceptions as noted below) ¹
	Grade 4	Off protocol therapy
Patients with Grade 2 or 3 N-V should be evaluated for upper GI inflammation and other immune related events.		
Neurologic events (new,	≤ Grade 1	No dose modification
	Grade 2	Hold until ≤ Grade 1 OR baseline (exceptions as noted below) ¹

Treatment-related Adverse Event	Grade of Event	Nivolumab and/or Ipilimumab
motor, sensory, encephalitis)	Grade 3	Off protocol therapy (exceptions as noted below) ¹
	Grade 4	Off protocol therapy
Fatigue	≤ Grade 1	No dose modification
	Grade 2	No dose modification
	≥Grade 3	Off protocol therapy (exceptions as noted below) ¹ – if fatigue is found related to endocrinopathy and clinical symptoms are managed with hormone replacement, patient resume therapy
	Grade 4	Off protocol therapy

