Distinguishing inflammatory pneumonitis is often a diagnosis of exclusion for patients who do not respond to antibiotics and have no causal organism identified including influenza. Most patients with respiratory failure or hypoxia will be treated with steroids. Bronchoscopy may be required and analysis of lavage fluid for lymphocytic predominance may be helpful. Patients with new lung nodules should be evaluated for sarcoid like granuloma. Please consider recommending seasonal influenza killed vaccine for all patients. Recommended management: See Pulmonary Adverse Event Management Algorithm		
Thrombocytopenia	≤ Grade 1	No dose modification
	Grade 2	Hold until ≤ Grade 1 OR baseline (exceptions as noted below) ¹
	Grade 3	Off protocol therapy
	Grade 4	Off protocol therapy
Neutropenia	≤ Grade 1	No dose modification
	Grade 2	Hold until ≤ Grade 1 OR baseline (exceptions as noted below) ¹
	Grade 3	Off protocol therapy
	Grade 4	Off protocol therapy
*Patients requiring a delay of >2 weeks must go off protocol therapy.		
Renal	≤ Grade 1	No dose modification
	Grade 2	Hold until ≤ Grade 1.
	Grade 3	Off protocol therapy
	Grade 4	Off protocol therapy
See Section 18.3 for Management recommendations. ⁵		
Endocrine Hypophysitis Adrenal Insufficiency	≤ Grade 1	No dose modification
	Grade 2	Hold until patients are on a stable replacement hormone regimen. If treated with steroids patients must be stable off steroids for two weeks.
Treatment-related Adverse Event	Grade of Event	Nivolumab and/or Ipilimumab
Endocrine Hypophysitis Adrenal Insufficiency (continued)	Grade 3	Hold until patients are on a stable replacement hormone regimen. If treated with steroids patients must be stable off steroids for two weeks.
	Grade 4	Off protocol therapy
Note all patients with symptomatic pituitary enlargement, exclusive of hormone deficiency, but including severe headache or enlarged pituitary on MRI should be considered Grade 3 events. Isolated thyroid or testosterone deficiency may be treated as Grade 2 if there are no other associated deficiencies and adrenal function is monitored. Please evaluate pituitary function before beginning steroid therapy or replacement therapy of any kind. *Note patients with thyroiditis may be retreated on replacement therapy. Patients must be evaluated to rule out pituitary disease prior to initiating thyroid replacement.		

Treatment-related Adverse Event	Grade of Event	Nivolumab and/or Ipilimumab

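### Steroid conditions for resuming or stopping study drug conflict or overlap across 8.3b-e, 8.4b-c, 8.7 and Table 8.1, with unclear scope and no explicit precedence rule

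*Combined protocol and SAP*

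**What the plan says.** All of the text is in protocol Section 8.

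- **8.3b** (section headed ipilimumab, Arm 1): "Events which require intervention with immunosuppressant therapy, steroids, surgery, or hormone replacement generally require permanently stopping study treatment".
- **8.3c** lists reasons for permanent discontinuation. One is an event needing immunosuppression or systemic steroids "which cannot be discontinued during the time in which it takes to hold more than 2 treatment doses".
- **8.3d** lists exceptions to permanent discontinuation. One, at the investigator's judgment, is a systemic steroid course shorter than two weeks in a patient with no sign of an autoimmune condition needing steroids. A note under the endocrinopathy exception reads: "Ipilimumab may not be restarted while the patient is being treated with systemic corticosteroids except for patients on stable doses of hormone replacement therapy".
- **8.3e** permits dose delays to manage drug-related events and gives long steroid tapers as an example.
- **8.4b** (Arm 2) covers patients who experience "immune-related toxicity with inability to decrease prednisone ≤ 10 mg PO daily must go off protocol therapy entirely".
- **8.4c** (Arm 2) says that patients who received systemic steroids for drug-related immune toxicity of any kind "must be off corticosteroids or have tapered down to an equivalent dose of prednisone 10 mg/day".
- **Table 8.1, diarrhea row**: "Patients who require steroids must be taken off study treatment".
- **Table 8.1, endocrine row, Grades 2 and 3**: "If treated with steroids patients must be stable off steroids for two weeks".
- **Table 8.1, pulmonary row, Grade 2**: needing steroids ends protocol therapy.
- **8.7, enterocolitis**: drug is withheld during evaluation, persistent cases start systemic steroids, and permanent discontinuation of both drugs is tied to severe disease.

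**The concern.** A site with a steroid-treated patient needs two answers: whether the steroid use itself ends treatment and, if not, what steroid status is required before the next dose. Section 8 answers both questions more than once, and the answers differ. It is also unclear which arm and which drug some of the answers cover.

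Re-exposure after an immune toxicity is a safety decision, so a protocol under which compliant sites can reach opposite decisions is a defect in itself. Doses given and off-treatment reasons would also be recorded inconsistently between sites. The protocol expects more toxicity with the combination (Background; Appendix 18.1), but two of the three conflicts below also arise in Arm 1.

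**Working it through.** The plan gives no figure to reproduce. The check is to fix the scope of each condition and then follow single patients through every passage that applies to them.

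**Scope**

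| Place | Arm and drug | Events | Effect of steroids |
|---|---|---|---|
| 8.3b | Arm 1 by heading | any | usually a permanent stop |
| 8.3c | Arm 1 by heading | any | stop only if steroids outlast a time limit |
| 8.3d, short course | Arm 1 by heading | any without autoimmune disease needing steroids | may continue |
| 8.3d, note | ipilimumab; arm unclear | placed under endocrinopathies | no restart on systemic steroids except stable replacement |
| 8.3e | mixed Arm 1 and Arm 2 text | any | delay for taper allowed |
| 8.4b-c | Arm 2 | any drug-related immune toxicity | off steroids or at 10 mg/day |
| Table 8.1, diarrhea | either drug | diarrhea/enterocolitis | off treatment |
| Table 8.1, pulmonary | either drug | Grade 2 | off treatment |
| Table 8.1, endocrine | either drug | Grades 2-3 | two weeks off steroids |
| 8.7 | both drugs | enterocolitis | permanent stop tied to severity |

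Table 8.1 binds Arm 1 as well as Arm 2: the opening of 8.3 sends ipilimumab dosing to it, and its column covers either drug.

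**(a) Arm 1, Grade 2 diarrhea, systemic steroids for under two weeks, no autoimmune disease requiring them.** Suppose the event settles before the row's separate two-week delay limit is reached.

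- 8.3d: the investigator may continue treatment.
- 8.7: a permanent stop is not called for, because the event is not severe. It gives no express permission to resume.
- Table 8.1: off treatment, because steroids were required.

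The result is continue or remove. Such a patient is foreseeable: the same table row allows retreatment after resolution when colonoscopy and biopsies are normal. The mismatch between 8.7 and the row also applies to Arm 2.

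**(b) Arm 1, Grade 2 hepatitis that resolves in time for a restart under 8.3b.** Suppose the steroid course lasts longer than two weeks but ends before a third dose would be held. With 21-day cycles, the third held dose falls 2 × 21 = 42 days after the first.

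- 8.3b: usually a permanent stop.
- 8.3c: the steroid criterion is not met.
- 8.3d: the short-course exception does not apply, since the course exceeds two weeks.
- 8.3e: a delay for the taper is allowed.
- Table 8.1, liver row: hold until Grade 1 or baseline, with no steroid condition.

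The result is resume or stop, with no exception in 8.3d that settles it.

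**(c) Arm 2, Grade 2 hepatitis resolved, prednisone 10 mg/day.**

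- 8.4b does not remove the patient, and the 8.4c condition is met.
- Table 8.1, liver row: no steroid condition.
- 8.3d note: ipilimumab may not restart, if the note reaches Arm 2 and events other than endocrinopathy.

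The result is dose ipilimumab or hold it. The heading of 8.3 points to Arm 1, but 8.3e coordinates nivolumab with ipilimumab, deals with Grade 2 events on the combination, and rules out ipilimumab monotherapy in Arm 2.

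**Rows stricter than 8.4c.** An Arm 2 patient with Grade 2 or 3 hypophysitis on prednisone 10 mg/day meets 8.4c but is held by the endocrine row. A Grade 2 pulmonary patient who needed steroids is removed by the pulmonary row whatever the taper. These rows differ from 8.4c but can stand beside it if 8.4c is only a necessary condition.

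**The case against.** The best defense is that these are layered rules of different scope. 8.3 and 8.4 call their own lists general and refer to Table 8.1 for each event type. 8.3b tells sites to follow event-specific guidance, and 8.4d defers to the table on permanent ipilimumab discontinuation. 8.4c is phrased as a requirement, so a stricter row merely adds to it. The stop in 8.3b is hedged and is followed by a list of exceptions. The 8.3d note sits under an Arm 1 heading and under one bullet on endocrinopathies.

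Much of this stands. A reader might infer that the protocol holds five incompatible versions of one rule. The documents do not support that: the conditions differ in arm, drug, event and grade, and none of the patients followed here meets them all. A reader might also take 8.4c as permission to resume at 10 mg/day. It states what must be true, not that dosing may follow, so the diarrhea, endocrine and pulmonary rows do not by themselves contradict it.

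The defense does not clear the three conflicts. The pointer toward event-specific guidance is a cue, not a precedence rule: it does not say whether an exception in 8.3d overrides a table row, or the reverse, and 8.7 is event-specific too. In (b) and (c) the liver row has no steroid condition, so deferring to it does not say whether 8.3b or the 8.3d note still applies. Whether 8.3 reaches Arm 2 cannot be settled from its text.

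**Conclusion.** The steroid conditions conflict or overlap, with unclear arm and drug scope and no explicit order of precedence. The consequence is continue or remove in (a), resume or stop in (b), and dose or hold ipilimumab in (c). Conflicts (a) and (b) arise wholly within Arm 1 and do not depend on the reach of 8.3. Conflict (c) depends on the 8.3d note reaching Arm 2 and non-endocrine events, which the text neither confirms nor excludes.

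Two further inferences are not supported. The first is a count of affected patients built on the 55% Grade 3/4 rate for the combination in Appendix 18.1. The documents give no share of patients treated with steroids, and Table 8.1 takes most Grade 3 and 4 events off protocol therapy in any case, subject to its footnotes and the nivolumab-alone provision in 8.4. The second is a distortion of the PFS comparison. Under 10.5, stopping for toxicity is not a PFS event, and 8.3e keeps disease assessments on schedule when dosing is delayed. No effect on alpha, power or bias can be derived. The point concerns internal consistency and patient safety, and that is enough to require correction.

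**What to change.** Reconcile 8.3b-e, 8.4b-c, the enterocolitis text of 8.7 and the steroid statements in Table 8.1 in one amendment to Section 8. A single table by event type and grade would do it, stating for each arm and drug:

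- whether steroid use alone ends treatment;
- what steroid status is required before the next dose;
- how hormone replacement is treated.

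The amendment should also say what 8.4c is a condition for, whether each part of 8.3 applies to Arm 2, and which passage prevails where two apply. The clinical content is for the study chairs, and this review takes no view on it. The cost is one amendment, with no change to sample size, assessments or analysis.

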Immune-mediated Hepatitis and Pancreatitis

Hepatic immune-related AEs were mostly clinically silent and manifested as transaminase or bilirubin laboratory abnormalities. Fatal hepatic failure has been reported in clinical trials of ipilimumab. Serum transaminase and bilirubin must be evaluated before each dose of ipilimumab and nivolumab as early laboratory changes may be indicative of emerging immune-related hepatitis/ pancreatitis and elevations in liver function tests (LFTs) **may develop in the absence of clinical symptoms**. Increase in LFT or total bilirubin should be evaluated to exclude other causes of hepatic injury, including infections, disease progression, or other medications, and monitored until resolution. Liver biopsies from patients who had immune-related hepatotoxicity showed evidence of acute inflammation (neutrophils, lymphocytes, and macrophages).

Monitor liver function tests (hepatic transaminase and bilirubin levels) and assess patients for signs and symptoms of hepatotoxicity/ pancreatitis before each dose of ipilimumab and nivolumab. In patients with hepatotoxicity, rule out infectious or malignant causes and increase frequency of liver function test monitoring until resolution. Withhold ipilimumab and nivolumab in patients with Grade 2 hepatotoxicity.

Permanently discontinue ipilimumab and nivolumab in patients with Grade 3–5 hepatotoxicity/pancreatitis and administer systemic corticosteroids at a dose of 1 to 2 mg/kg/day of prednisone or equivalent. When liver function tests show sustained improvement or return to baseline, initiate corticosteroid tapering and continue to taper over 1 month. Across the clinical development program for ipilimumab, mycophenolate

treatment has been administered in patients who have persistent severe hepatitis despite high-dose corticosteroids.

Immune-mediated Dermatitis

Skin immune-related AEs presented mostly frequently as a rash and/or pruritus. Some patients reported vitiligo associated with ipilimumab administration. Fatal toxic epidermal necrolysis has been reported in clinical trials of ipilimumab.

Monitor patients for signs and symptoms of dermatitis such as rash and pruritus. Unless an alternate etiology has been identified, signs or symptoms of dermatitis should be considered immune-mediated.

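### For Arm 2, Section 8.4d lets nivolumab continue while an adverse event is unresolved, most Grade 2 rows of Table 8.1 hold it, and no order of precedence is stated

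*Combined protocol and SAP*

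**What the plan says.** Two places carry the conflict.

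- **Section 8.4d** (Arm 2): "Nivolumab monotherapy may be continued at treating investigator discretion if there is evidence of clinical benefit". It then says that in this case the "patient will continue nivolumab until AE is resolved and ipilimumab may be re-started". An alternative branch covers patients whose ipilimumab is stopped for good. No grade is named.
- **Table 8.1**: one instruction column, headed "Nivolumab and/or Ipilimumab". The usual Grade 2 entry is "Hold until ≤ Grade 1 OR baseline (exceptions as noted below").

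Three others bear on it less directly.

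- **Opening of 8.4**: in the induction period, patients whose Grade 2 or 3 event requires stopping the combination "may consider continuing treatment with single agent nivolumab when the event resolves to baseline".
- **Section 8.7**, hepatitis and pancreatitis: "Withhold ipilimumab and nivolumab in patients with Grade 2 hepatotoxicity". No release rule follows.
- **Section 8.3e**, which sits under the Arm 1 heading but speaks of the combination: "In event of any Grade 2 adverse event experienced while on combination nivolumab plus ipilimumab therapy", the "patient may resume treatment/may be continued on nivolumab monotherapy alone, at the discretion of the treating investigator".

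**The concern.** In 8.4d, resolution of the event is the trigger for restarting ipilimumab, and nivolumab is given up to that point. Table 8.1 makes improvement of the event the condition for giving either drug. For an event that is still Grade 2 on a dosing day, the first permits nivolumab and the second holds it.

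The first stake is safety, because the question is whether a checkpoint inhibitor is infused during an active and possibly immune-mediated event. The second is the data. Nivolumab exposure in the experimental arm, and the Arm 2 toxicity profile that is a secondary objective (1.2d), would depend partly on which page a site follows.

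Retention on treatment may also be touched. In the nausea, diarrhea, vomiting and neutropenia rows, a delay of more than 2 weeks takes the patient off protocol therapy. The plan does not say whether a patient given nivolumab alone meanwhile counts as delayed.

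**Working it through.** No sample size, alpha or event count is involved. The check is a count of the table rows and a side-by-side reading.

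**Step 1. What Table 8.1 does at Grade 2, row by row.**

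| Grade 2 instruction | Rows | Number |
|---|---|---|
| Hold to Grade 1 or lower, or baseline | nausea; diarrhea; vomiting; other GI; neurologic; skin; thrombocytopenia; neutropenia; liver function; amylase or lipase; all other events | 11 |
| Hold to Grade 1 or lower | fever; renal | 2 |
| Own hold or interruption rule | pneumonitis; endocrine; cardiac; infusion reaction | 4 |
| No hold | fatigue; any other laboratory abnormality | 2 |

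Total: 11 + 2 + 4 + 2 = 19 rows. Rows that hold until the event improves to a stated grade: 11 + 2 = 13. The catch-all row for all other events is one of the 13, so events not listed by name are held as well.

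**Step 2. Does the table hold nivolumab, or only ipilimumab?** There is no separate nivolumab column. Section 8.4a adds investigator-judged delays to those in the table and names both drugs when it does so, which reads the table's holds as covering both.

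**Step 3. Is there an exception for nivolumab alone?** Footnote 1 covers three things: Grade 2 ocular events that do not respond to topical therapy or need systemic treatment; any event judged a substantial clinical risk; and Grade 3 or 4 laboratory abnormalities manageable apart from organ pathology. None permits nivolumab alone during an ongoing Grade 2 event.

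**Step 4. Does 8.4d defer to the table?** It refers to the table once, in the branch where ipilimumab is permanently discontinued. The branch that continues nivolumab until resolution carries no such reference.

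**Step 5. One patient under each passage.** Take an Arm 2 patient due an induction dose, with an ongoing Grade 2 transaminase rise, whom the investigator judges to be benefiting.

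- 8.4d: nivolumab alone may be given.
- Table 8.1, liver row: held until Grade 1 or lower, or baseline.
- 8.7: both drugs withheld; no statement of when to restart.
- 8.3e: nivolumab alone may be resumed or continued; silent on whether the event must have resolved.
- 8.4 opening: applies only if the event requires stopping the combination; single-agent nivolumab is then tied to return to baseline.

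The first two give opposite answers for the same dose. The other three do not settle which prevails.

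**The case against.** The best defence is structural. Section 8.4 says that modifications by event type are in Table 8.1 and offers items a to d as general considerations. On that footing 8.4d could work inside the table: hold to Grade 1, then give nivolumab alone until the event has fully resolved and ipilimumab restarts. The column heading, with its and/or, might also let a site hold one drug and give the other. This reading is possible but strained. The table releases both drugs at the same threshold, so it leaves no interval in which only nivolumab is allowed, and nothing in 8.4d says that a hold comes first.

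Second, 8.4d is limited. It is discretionary and needs evidence of clinical benefit. Section 8.4a lets the investigator delay for any event. Section 8.4c requires patients treated with systemic steroids for drug-related immune toxicity to be off them or down to the equivalent of prednisone 10 mg/day. Footnote 1 removes patients at substantial clinical risk. These limits stand and narrow the exposure to harm. They do not tell a site what to do with a Grade 2 event that triggers none of them.

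Third, the supporting passages are weaker than they look, and this objection stands in full. In 8.3e, resuming implies an earlier hold, and its first bullet assumes that both drugs had been held; only the alternative of continuing points the other way. The 8.4 opening concerns events that require stopping the combination, not a temporary pause of ipilimumab. Section 8.7 withholds for enterocolitis and neuropathy only pending evaluation, and gives no restart rule for Grade 2 hepatotoxicity.

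Finally, the flow charts in Appendices 18.3 and 18.4 were not visible in the text used for this check. They may carry a hold rule for nivolumab.

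**Conclusion.** The contradiction between 8.4d and the Grade 2 hold rows of Table 8.1 is real, and no explicit precedence resolves it. It reaches 13 of the 19 event rows. It does not reach Grade 2 fatigue or other laboratory abnormalities, which are not held, and the four rows with their own rules need separate reading. The conclusion rests on taking 8.4d at its plain meaning and on applying it to Grade 2 events, although it names no grade.

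A reader might infer more, and the documents do not support it:

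- **That all five passages collide head-on.** Section 8.3e does not clearly permit dosing through an unresolved event, 8.7 does not say that drug is withheld until resolution, and the 8.4 opening addresses a narrower group. They are tensions to align.
- **That each hold costs one of the four induction doses.** For Arm 2 the plan provides for delay (8.2b, 8.4); a held dose need not be a lost one.
- **That the number of patients can be estimated.** No Grade 2 rate is given. The 55% in Appendix 18.1a is a Grade 3/4 rate and says nothing about Grade 2 holds.
- **That the PFS comparison is biased.** No effect on PFS can be shown from the documents. What follows is possible variation between sites in Arm 2 exposure and toxicity, of unknown size.

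The point should be fixed because it concerns dosing during an active event and is cheap to remove.

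**What to change.** Reconcile 8.4d with the Grade 2 rows of Table 8.1. One statement, by event type if needed, should say whether nivolumab is given or held while a Grade 2 event is unresolved, and which passage takes precedence. Align 8.3e, the 8.4 opening and 8.7 to it by cross-reference, and check the 18.3 and 18.4 flow charts against it. Which rule applies is a clinical decision for the study chairs; no view is taken here.

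The cost is a short protocol clarification. Sample size, alpha and the analysis plan are untouched.
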